11.1.3. Vital Signs

Vital signs will include systolic and diastolic blood pressure, heart rate, respiration rate, body temperature, and pulse oximetry, and will be measured after the subject has been resting in a supine position for at least 5 minutes. Vital signs will be performed at screening, Day -1, Day 1 (prior to dosing, at 5, 10, 15, 30, and 45 minutes, and at 1, 1.5, 3, 5, 8, and 12 hours after dosing), Day 2 (24 hours post-dose \pm 1 hour), Day 3 (48 hours post dose \pm 1 hour), and Day 8. Vital signs may be taken at other times if deemed necessary by the investigator or site SOPs.

In addition, starting at 1 hour prior to dosing on Day 1, vital signs (excluding body temperature) will be continuously monitored for 24 hours post dose (refer to Section [11.1.2](#) for details).

Where the time of vital signs monitoring coincides with a blood draw, vital signs will be performed within 5 minutes prior to the nominal time point (refer to Section [11.1](#) for details).

11.1.4. Weight and Height

Subjects will have a height (cm; screening only) and weight (kg) measurement during screening with BMI calculation, a weight measurement on Day -1 with BMI calculation, and a weight measurement only on Days 3 and 8. The Day -1 weight will be used for dose determination.

11.1.5. Physical Examination

Each subject will have a complete physical examination at screening, Day -1, and Day 8. Abbreviated (targeted) physical examinations will be performed as needed prior to dosing on Day 1 and prior to discharge on Day 3. A complete physical examination includes all major systems, including general appearance, EENT, chest/respiratory, heart/cardiovascular, abdomen/gastrointestinal, lymph nodes/spleen, genitourinary, musculoskeletal, skin, neurological, and hepatic. The screening physical exam includes an assessment of upper leg

muscle tissue (ie, adequacy of tissue for IM injection). Targeted physical examinations may be performed at other times as deemed necessary by the investigator.

In addition, at the request of the DSMB for Cohorts 3-5, a brief neurological assessment will be performed at 1 hour post dosing (+30 min) on Day 1 to assess alertness/level of consciousness, orientation, ability to follow commands and coordination. The assessment will be documented in the subject's medical record. At the end of each cohort, the PI will provide narratives (per cohort and subject) for inclusion in the DSMB data reviews.

The brief neurological assessment will be performed as follows in this sequence:

- 1) To assess alertness and level of consciousness, the RASS ([Appendix D](#)) will be employed and the completed scale will be added to the subject's medical record.
The RASS score will be entered into the eCRF; however, the scores for orientation and ability to follow commands (see below) will not be entered into the eCRF.
- 2) Orientation will be assessed using questions 1 and 2 of the Folstein Mini-Mental Status Examination ([Rovner and Folstein, 1987](#)), as shown below. The answers to each question will be noted in the subject's medical record, along with the combined score for the two questions. Scoring will be performed according to Rovner and Folstein ([1987](#)).
 - “What is the year? Season? Date? Day of the week? Month?”
 - “Where are we now: State? County? Town/city? Hospital? Floor?”
- 3) Ability to follow commands and coordination (to the extent possible) will be assessed using a modified question 8 of the Folstein Mini-Mental Status Examination as shown below. The total score will be noted in the subject's medical record. Scoring will be performed according to Rovner and Folstein ([1987](#)).
 - “Take the paper in your right hand, fold it in half, and hand it back to me.”
(The examiner gives the patient a piece of blank paper).

11.1.6. Neuropsychiatric/Behavioral/Cognitive Assessments

The SCID-5-CT (customized) ([First et al-2015](#)) will be administered by a psychologist at Day-1 as a screening tool to exclude any subjects with major DSM-5 Axis I or II disorders. Due to the nature of the assessment, the SCID should not be repeated during this study. Therefore, for any subject who receives the SCID on Day -1, but is subsequently designated an alternate and readmitted on another day, the initial SCID will serve as their assessment of record.

Other assessments of neuropsychiatric/behavioral symptoms will be performed by appropriately experienced and trained study staff using the C-SSRS ([Posner et al-2011](#)), BPRS (expanded version 4.0, 24 items) ([Ventura et al-1993](#)), and RASS ([Sessler et al-2002](#), [Ely et al-2003](#)). A psychiatrist will be available by phone to consult with the investigator throughout the study. At the investigator's request, the psychiatrist will come to the clinic to evaluate a subject.

The C-SSRS Baseline/Screening version will be administered by study staff at screening, and the C-SSRS Since Last Visit version will be administered at Day -1 and at follow-up on Day 8.

Scoring and analysis will be performed according to the Columbia-Suicide Severity Rating Scale Scoring and Data Analysis Guide. Study staff administering the C-SSRS will complete C-SSRS training.

The BPRS will be performed by a psychologist or trained clinician at screening, Day -1 (baseline), at 6 (+ 2) hours post dose (timing at the discretion of the investigator), 48 hours post dose (prior to discharge), and on Day 8. For BPRS items assessed over time (eg, items 1, 2, and 3), the period of assessment should be over the prior week, except for assessments performed at 6 and 48 hours post dose, which will be assessed since the prior assessment. The + 2-hour window for the 6-hour post-dose BPRS is intended to allow the investigator some discretion should the assessment need to be delayed. The timing may be dependent on the emergence and severity of neuropsychiatric symptoms. If the investigator determines a subject is incapable of providing valid responses during the + 2-hour window, the reason(s) why the BPRS was delayed or could not be done will be documented in the source documentation.

Mental health/behavioral symptoms, judged to be clinically significant, should be reported as AEs at whatever time point they may be observed. As part of the reporting process, if the AE corresponds to an item on the BPRS, the relevant item on the BPRS scale should be used for assessing the severity of the event. In addition, if AEs of general agitation or sedation are reported, since these do not correspond to a specific item on the BPRS, the RASS should be used by a physician, physician assistant, or nurse to assess severity (see [Appendix D](#)).

The DSST ([Strauss et al-2006](#)) will be administered by appropriately trained study staff at screening, baseline (Day -1), 48 hours post dose (Day 3), and Day 8 to detect any persistent cognitive effects. The screening time point is included to reduce practice effects between baseline and re-administrations thereafter. The DSST will not be used to determine eligibility.

Note: Alternates who are readmitted on another day will have the BPRS, C-SSRS, and DSST repeated.

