Inclusion/Exclusion		X	X	X ^d					
Medical History including Demography		X	X						
Physical or Brief Neurological Examination		X	X	X ^e		X ^e		X	
Serum Pregnancy Test		X	X					X	
Laboratory Safety Tests ^f		X	X		X	X		X	
Serology ^g		X							
Urine Drug Screen ^h		X	X					X	
Alcohol Breathalyzer Test		X	X						
Body Weight and Height/Body Mass Index		X ⁱ	X ⁱ			X ⁱ		X ⁱ	
Vital Signs ^j		X	X	X	X	X		X	
Electrocardiogram (ECG), 12-lead (supine) ^k		X	X	X	X	X		X	
Dose Administration				X					
Pharmacokinetic Assessment				X ^l	X	X			
Adverse Events				X ^m	X	X	X	X	X
Prior/Concomitant Medications		X	X	X	X	X	X	X	X
Continuous Cardiovascular Monitoring				X ⁿ	X ⁿ				
Injection Site Assessment ^o				X	X	X		X	
Injection Site: VAS ^o				X	X	X		X	
Reminder of Study Restrictions		X				X	X	X	

Table 3: Study Events Schedule (Continued)

Study Phase	Screening	Baseline ^a	Treatment ^a			Follow-up ^b		
Study Day	-30 to -2	-1	1 ^c	2 (24 ± 1 h)	3 (48 ± 1 h)	4 (+ 2 days)	8 (+2 days)	30 (+ 7 days)
Procedures								
Brief Psychiatric Rating Scale (BPRS) ^d	X	X	X		X		X	
Columbia-Suicide Severity Rating Scale (C-SSRS) ^e	X	X					X	
Richmond Agitation and Sedation Scale (RASS)				X ^r				
Structured Clinical Interview for DSM-5, Clinical Trial version (SCID-5-CT)		X ^s						
Digit Symbol Substitution Test ^t	X	X			X		X	

^a Subjects will be in clinic for the baseline and treatment days. Days 2 and 3 procedures should be performed at 24 and 48 hours (± 1 hour) post dose, respectively, except for PK samples, which should be collected as close to the specified time points as possible. Refer to [Table 4](#) for expansion of pre-dose through 36-hour post-dose activities.

^b Day 4 and Day 30 follow-up is conducted by telephone. Day 4 follow-up may be performed on Days 4-6. Day 30 follow-up may be performed on Days 30-37. Day 8 follow-up is an in-clinic visit and may be performed on Days 8-10. Note: Subjects who withdraw/are withdrawn after receiving study drug will undergo all Day 8 follow-up procedures, including pregnancy testing for females, if possible.

^c See [Table 4](#) for study events occurring pre dose through 36 hours post dose.

^d Final eligibility criteria review and completion of eligibility checklist prior to dosing.

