ⁿ Continuous cardiovascular monitoring of ECG (3-lead) and vital signs (blood pressure (at 5-15 min intervals), heart rate, respiration rate, and pulse oximetry) from 1 hour prior to dosing through 24 hours post dose (see [Table 4](#) and Section [11.1.2](#) for details).

^o Injection site assessments: Subject will be asked to rate the maximum intensity of pain, pruritus, tingling, and numbness using the VAS. See [Table 4](#) for assessment time points from pre dose through 24 hours post dose. Immediately following the subjective assessment, an assessment of pain, tenderness, erythema, and induration at the injection site will be performed by a physician, physician assistant, or nurse.

^p See [Table 4](#) for assessment time points on Day 1. For items assessed over time (eg, items 1, 2, and 3), the period of assessment should be “over the prior week,” except for the assessments performed at 6-8 and 48 hours post dose, which should be assessed “since the prior assessment.”

^q C-SSRS will be assessed at screening, Day -1 (baseline), and Day 8.

^r RASS will be used to assess alertness/level of consciousness at 1 hour post dosing (+30 min) (see footnote ^e above), and at other times for severity if AEs of general agitation or sedation occur.

^s SCID-5-CT will be administered at Day -1 to identify the presence of any major DSM-5 Axis I or II disorder. Note: Alternates who return for dosing on another day will not have the SCID repeated.

^t The DSST will be administered at screening, baseline, 48 hours post dose, and Day 8 to detect any persistent cognitive impairment. The DSST will not be used to determine eligibility.

Table 4: Study Events Schedule – Pre Dose through 36 Hours Post Dose

Activity/Assessment	Pre Dose	Dosing = Time 0	Minutes Post-dose							Hours Post-dose									
			2	5	10	15	20	30	45	1	1.5	2	3	4	5	8	12	24	36
ECG	X			X	X	X		X	X	X	X		X		X	X	X	X	
Vital Signs	X			X	X	X		X	X	X	X		X		X	X	X	X	
Abbreviated Physical or Brief Neurological Exam ^a	X									X									
Injection Site: VAS ^b	X			X	X	X		X	X	X	X		X		X	X	X	X	
Injection Site: Physician, Physician Assistant or Nurse	X			X	X	X		X	X	X	X		X		X	X	X	X	
BPRS ^c																			6
C-SSRS																			
RASS ^d			At 1 hour post-dosing (+30 min) and as needed to assess severity only if adverse events of general agitation or sedation occur																
Final Eligibility	X																		
Eligibility Checklist	X																		
Randomization	X																		

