7.6.1.2. Nonextreme Dose-Limiting Toxicities

Nonextreme DLTs are AEs that do not meet the criteria for extreme DLTs but are serious conditions that require immediate medical attention and monitoring. The incidence and severity of these events will be used to determine whether (1) the total cohort size will be increased from 8 to 12 and (2) the need to suspend dosing until the DSMB has completed a safety review and made a recommendation to the sponsor ([Table 6](#)). Nonextreme DLTs include:

- Respiratory
 - Spontaneous respiratory rate < 8 or > 25 breaths per minute, with oxygen saturation less than 90%, which cannot be explained by agitation or other behavioral symptoms and that does not respond immediately to oxygen supplementation via nasal cannula or face mask but for which there is recovery without sequelae prior to the need for intubation
 - Dyspnea at rest
 - Symptomatic bronchospasm
- Neuropsychiatric
 - Neuropsychiatric symptoms (eg, delirium, paranoia, and/or hallucinations) requiring treatment with physostigmine or other medication(s) and, in the opinion of the investigator, responded adequately to treatment
 - Persistent neuropsychiatric symptoms, defined as a score of 4 or higher on any one item or a total score of 40 or higher on the BPRS assessment at the 48-hour, post-dose evaluation
 - Paresthesia that interferes with any activity
 - Athetoid movement
- Cardiac
 - Hypertension, which cannot be explained by agitation or other behavioral symptoms, requiring antihypertensive medication
 - Cardiac arrhythmias or changes that are deemed clinically significant but do not cause the subject to be hemodynamically unstable
 - QTc is > 450 msec for males or > 470 msec for females and has increased > 60 msec from baseline
 - Supraventricular tachycardia alone without hemodynamic compromise
 - Bigeminy or trigeminy not associated with hypotension
- Renal
 - Increase of serum creatinine by ≥ 0.3 mg/dL (≥ 26.4 μ mol/L) or increase to $\geq 150\%$ from baseline or urine output < 0.5 mL/kg/hour for > 6 hours
- Injection Site Reaction

- Any reaction determined to be severe, as defined by the FDA's guidance for injection site reactions ([Appendix B](#)).

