5.1.8 Neuropsychiatric/Behavioral Assessments

Assessments of neuropsychiatric/behavioral symptoms will be performed by study staff using the C-SSRS, BPRS (expanded version 4.0, 24 items), and RASS (if general agitation or sedation are reported). A psychiatrist will be available on-site to consult with the investigator throughout the study. At the investigator's request, the psychiatrist will come to the clinic to evaluate a subject.

The C-SSRS Baseline/Screening version will be administered by a physician, physician assistant, or nurse at screening, and the C-SSRS Since Last Visit version will be administered at SD -1 and at follow-up on SD 8. Scoring and analysis will be performed according to the Columbia-Suicide Severity Rating Scale Scoring and Data Analysis Guide. Study staff administering the C-SSRS will complete C-SSRS training. The C-SSRS has excellent inter-rater reliability².

The BPRS will be performed by a psychologist or trained clinician. The BPRS will be assessed at screening, SD -1 (baseline), at 6 (+ 2) hours post dose (timing at the discretion of the investigator or designee), 48 hours post dose (prior to discharge), and on SD 8. In order to improve reliability between administrations, a structured interview guide will be used and the same clinician will administer the BPRS to each participant. For BPRS items assessed over time (e.g., items #1, 2, and 3), the reference period of assessment should be over the prior week, except for assessments performed at 6 and 48 hours post dose, which will be assessed since the prior assessment. The BPRS has low inter-rated reliability, and measures will be taken to ensure that it is captured consistently over time.

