6.3 HYPOTHESES AND DECISION RULES

As the objective of this study is to characterize the safety and tolerability of escalating doses of Scop HBT, three sets of safety endpoints will be compared statistically between placebo and active dosing groups. Some PK parameters will also be compared statistically across dose levels. Table 7 describes the hypothesis testing pre-specified in the statistical analysis.

The null hypothesis of no worse scores for Injection Site VAS (pain, itching, tingling, numbness); change in BPRS Score (6 hours, 48 hours, 8 days); change in DSST (48 hours, 8 days); and C-SSRS (SD 8) between dose levels of active Scop HBT and placebo will be tested statistically using a one-sided alternative of worse (higher for C-SSRS, VAS, and BPRS, lower for DSST scores for Scop HBT vs. placebo). Each dose level will be tested against the same placebo group (all participants receiving placebo). Methods for analysis of neuropsychiatric scales and injection site reactions are described in Sections 6.13.4 [6.14.6](#) and [6.14.8](#), respectively.

For PK parameters, variation across doses will be tested for T_{max} , $t_{1/2}$, V_d/F , Cl_F , and MRT against the null hypothesis of no difference across doses. A joint significance test (1 test per parameter) will be used.

Dose-proportionality will be tested using the dose-normalized parameters $C_{max}/Dose$ and $AUC_{\infty}/Dose$. A likelihood ratio test will be used for testing the joint null hypothesis of equivalence across all doses using a two-sided alternative. Each dose level will also be tested against the next dose level using a two-sided test. The methods for analysis and hypothesis testing are described in Section - [6.15](#). A total of 110 hypothesis tests will be performed. Procedures for multiple comparisons are detailed in Section [6.8](#).

Table 7: Pre-Specified Hypothesis Tests

Drug Characteristic	Null Hypothesis	Relevant Endpoints [Count]	Number of Comparisons Per Parameter	Total Number of Hypothesis Tests
Safety	Equivalence with Placebo	Injection site VAS (pain, itching, tingling, numbness) x (10-45 minutes, 1-5 hours, 8-48 hours) [12] Change in BPRS score from baseline (6 hours, 48 hours, SD 8) [3] Change in DSST scores from baseline (48 hours, SD 8) [2]	5 (Each dose level vs. Placebo)	90

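### The BPRS look-back periods let resolved acute symptoms into the Day 8 test (depending on visit day) and into the 48-hour *persistent* DLT criterion

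*Protocol*

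**What the plan says.** Protocol 11.1.6 sets the rating period for part of the scale, the items rated over an interval (1, 2 and 3 are named only as examples): "the period of assessment should be over the prior week, except for assessments performed at 6 and 48 hours post dose". Those two ratings instead cover the time from the previous assessment. Protocol Table 3 footnote p repeats the rule, giving the first exception as 6-8 hours. SAP Table 1 footnote p and SAP 5.1.8 carry it over. Screening, Day -1 and Day 8 therefore keep the one-week period.

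Dosing is on Day 1 (Protocol 7.5). On the later visit, Table 3 footnote b says "Day 8 follow-up is an in-clinic visit and may be performed on Days 8-10". The post-dose rating is due at 6 hours with a window of +2 hours. Table 4 footnote c and 11.1.6 allow for it not being done, with the reason documented.

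Protocol 7.6.1.2, repeated in SAP 5.1.2, lists as a nonextreme DLT "Persistent neuropsychiatric symptoms, defined as a score of 4 or higher on any one item or a total score of 40 or higher" when the scale is rated 48 hours after dosing. Nonextreme DLTs feed the halting rules in Protocol Table 6, the maximum tolerated dose in 7.6.1 and the upper bounds in SAP 6.4. Separately, Protocol 12.1.2 and SAP 6.3 test the BPRS change from baseline at 6 hours, 48 hours and Day 8 against placebo, one-sided, for each dose level.

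**The concern.** The 48-hour and Day 8 ratings are read as evidence of whether neuropsychiatric effects linger, but the rating instruction makes some items cover time when the drug was acting.

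At Day 8 this affects a hypothesis test. A subject seen on Day 8 can be scored for symptoms on the dosing day, while a subject with the same course seen on Day 10 cannot. Pooled placebo does not cancel this, because placebo subjects have no drug effect to be rated retrospectively.

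At 48 hours it affects a safety count. Neither document requires the symptom to be present at 48 hours, so a symptom that ended earlier in the interval can meet a definition headed *persistent*. That count bears on cohort expansion, halting, the maximum tolerated dose and the reported upper bounds. The overlap is widest for subjects too unwell for the 6-8 hour rating, who are likely to be the most affected.

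**Working it through.** The plan gives no figure for this point, so there is none to reproduce. The check is window arithmetic followed by labelled illustrations.

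**1. Look-back windows (nominal times).**

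| Rating | Period starts | Post-dose time covered |
|---|---|---|
| 48 h, earlier rating at 6 h | 6 h | 48 − 6 = 42 h (88% of 48 h) |
| 48 h, earlier rating at 8 h | 8 h | 48 − 8 = 40 h (83%) |
| 48 h, earlier rating missed | Day -1 | all 48 h |
| Visit on Day 8 | 8 − 7 = Day 1 | from about 0 h |
| Visit on Day 9 | 9 − 7 = Day 2 | from about 24 h |
| Visit on Day 10 | 10 − 7 = Day 3 | from about 48 h |

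The last three rows shift with the clock time of the visit.

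**2. Is acute effect after 6-8 hours plausible?** Protocol 5.2.4 quotes a half-life of about 220 minutes (subcutaneous data). The fraction left is 2^(−t/220 min): 32% at 6 h, 22% at 8 h, 1% at 24 h and 0.01% at 48 h. At the top dose, 0.021 × 0.32 = 0.0068 and 0.021 × 0.22 = 0.0046 mg/kg. That is near the 0.005-0.007 mg/kg range that Protocol 5.3.1.2 links to confusion and occasional delirium or hallucinations. One-compartment decay is only a rough scale. Protocol 5.2.4 also reports that several CNS effects lag plasma, with equilibration half-lives of 2.5 to 3.5 hours. The 48-hour window therefore includes a period of plausible effect, although almost no drug remains at its end.

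**3. Day 8 test, illustration.** These inputs are assumptions, not from the documents:
- every subject has recovered;
- every visit falls on Day 8;
- change-score SD is 1 (24 items each scored at least 1 give a floor of 24, and eligibility requires 25 or less);
- a fraction q of active subjects is rated 6 points higher through the look-back;
- nobody is censored for rescue.

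One dose level is compared with pooled placebo (2 × 5 = 10, or 3 × 5 = 15) by an unequal-variance t test, one-sided 0.05, simulated:

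| Active vs placebo | q = 0 | 10% | 25% | 50% |
|---|---|---|---|---|
| 6 vs 10 | 5% | 6% | 18% | 57% |
| 9 vs 15 | 5% | 10% | 34% | 82% |

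**4. DLT count at 48 hours.** SAP Table 8 shows what one more counted subject does with 6 active: the upper bound moves from 0.32 (no events) to 0.51 (one) and 0.67 (two).

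For Table 6, let q now be the assumed chance that an active subject has a resolved symptom counted this way and is not already a DLT. Under SAP 3.6 the first four subjects include a = 2 active with probability 2/6 = 1/3, otherwise a = 3. The dosing-halt threshold is one event in the first four or two in the first eight:

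P = 1 − (1−q)^a × [(1−q)^(6−a) + (6−a) q (1−q)^(5−a)].

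For q = 20%: a = 2 gives 0.476 and a = 3 gives 0.541, so P = 0.476/3 + 2 × 0.541/3 = 0.52. For q = 5% and 10%, P is 14% and 27%. The chance of three or more among six is 0.2%, 1.6% and 9.9% for q = 5%, 10% and 20%.

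**The case against.** **Which items are affected is not stated.** The look-back covers only items assessed over time, with items 1, 2 and 3 as examples. A reader might infer that anyone who hallucinated at 10 hours and was well by 20 hours becomes a DLT. The documents do not support that: Protocol 9.2.1 numbers hallucinations as item 10, and nothing says item 10 uses a look-back. This stands, and it limits what can be said about size.

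**Rescue treatment takes out part of the problem.** Under Protocol 9.2.1, a score of 5 or more on any of five BPRS items indicates physostigmine, and a treated event is already a DLT. Protocol 13.1 and SAP 6.11 then censor later BPRS data from the analysis. For those subjects the look-back adds no DLT and does not bias the tests. This stands. It leaves unrescued subjects, and it does not change the DLT definition.

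**Larger error rates come from the wrong test.** A pooled-variance t test in the same scenario gives about 15%, 40% and 79% for 6 against 10, and a reader might quote those. Protocol 12.5 and SAP 6.10 call for unequal-variance methods when equal variances are rejected, and here the active arm is more variable by construction. At 10% affected, the excess with 6 active nearly disappears.

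**Other data distinguish resolved from lingering symptoms.** Clinically significant symptoms are recorded as AEs whenever observed (Protocol 11.1.6), and SAP 6.14.6 presents scores over time around a BPRS-defined event. A reader might infer that the trial cannot tell the two apart. That goes too far: DSMB and sponsor review can use these records. The DLT count and the test itself still do not make the distinction.

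**A broad definition may be deliberate.** That is possible, and it is for the sponsor to say. The two passages then need to agree.

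**Conclusion.** The concern holds, within limits. For the unlisted interval-rated items, the Day 8 comparison with placebo can pick up symptoms that have resolved, and whether it does depends on the visit day within Days 8-10. At 48 hours the same kind of symptom can meet a criterion labelled persistent.

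The two parts should be kept separate. A reader might infer that the Day 8 rating can also create a DLT, but only the 48-hour rating has a threshold. Nor does a counted nonextreme DLT end the trial: Table 6 leads to a halt, review and a sponsor decision.

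The timing follows directly from the text. The size does not. The illustrative rates rest on an assumed carry-over, SD and affected fraction, ignore rescue censoring and place every visit on Day 8; they show direction and a possible range only. This should be fixed, with medium confidence, and it does not by itself make the plan unworkable.

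**What to change.** - **Day 8 period.** In Protocol 11.1.6, Protocol Table 3 footnote p, SAP Table 1 footnote p and SAP 5.1.8, start the Day 8 reference period at the 48-hour assessment. It then excludes the dosing day for every visit on Days 8-10.
- **48-hour record.** For each item scored 4 or more, record whether the symptom is present at interview or occurred only earlier in the look-back.
- **Reporting.** In SAP 6.4, give the BPRS-based nonextreme DLT count and its upper bound both ways: all such scores, and only those with the symptom present at 48 hours.
- **Reconciliation.** The sponsor should reconcile *persistent* in Protocol 7.6.1.2 and SAP 5.1.2 with the since-prior-assessment instruction, including when the 6-8 hour rating is missing. Which events count as a DLT is the sponsor's decision.
- **Illustrations.** Any quoted size should use the planned unequal-variance methods and apply the rescue censoring.

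The cost is a short wording change in both documents and one tick-box per high-scoring item, with no extra visits. The drawback is that the Day 8 period no longer matches the one-week baseline period, which applies equally in both arms. Acute symptoms are still captured as AEs under Protocol 11.1.6.
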